1.3.4.1 Infusion Reactions and Hypersensitivity Reactions (including Anaphylaxis)

In Phase I/II clinical trials of GA101 - Obinutuzumab, the most common AEs were mild or moderate IRRs. To date, the commonly experienced IRRs are characterized, among other symptoms, by fever, chills, nausea, vomiting, hypotension, and fatigue.

Ibrutinib + GA101 - Obinutuzumab. University of California, San Diego

infusion-related Respiratory symptoms such as hypoxia, dyspnea, bronchospasm, larynx and throat irritation, and laryngeal edema have also been reported. These IRRs were mostly mild or moderate (NCI-CTC, v3.0, Grade 1-2), occurring predominantly during the first hour or shortly after the first infusion, and resolved with the slowing down or the interruption of the infusion and with supportive care where appropriate. In some subjects, some IRRs occurred up to 24 hours after receiving the first infusion. The incidence and severity of IRRs decreased with subsequent infusions. Cases of tumor flare have also been reported with GA101 -Obinutuzumab. Extensive tumor burden, predominantly localized in the blood circulation (e.g., high peripheral lymphocyte count in CLL subjects), may be a predisposing factor for the development of IRRs.

The mechanism of IRRs is unclear, but it is potentially linked to the process of B-cell depletion by ADCC and the rapidity of apoptosis. IRRs may be clinically indistinguishable from IgE-mediated allergic or anaphylactic reactions.

For the management of IRRs, see Section 6.1.12, For dose delay and modification instructions, see Section 6.1.4.

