6.2.6 Split Dosing

On Cycle 1, Day 1, 100 mg GA101-Obinutuzumab will be administered. On Cycle 1, Day 2, 900 mg of GA101-Obinutuzumab will be administered. On Cycle 1, Ibrutinib + GA101 – Obinutuzumab. University of California, San Diego

Days 8 and 15, and Day 1 of Cycles 2-6, 1,000 mg of GA101-Obinutuzumab will be administered (see Table 1).

Table 1 GA101 - Obinutuzumab Dosing Schedule

Cycle and Day of Administration		Dose of Obinutuzumab	Rate of Infusion (in the Absence of Infusion Reactions/ Hypersensitivity during Previous Infusions)	
	Day 1 100 m		Administer at 25 mg/hour over 4 hours. Do not increase the infusion rate.	
Cycle 1	Day 2	900 mg	Administer at 50 mg/hour. The rate of the infusion can be escalated in increments of 50 mg/hour every 30 minutes to a maximum rate of 400 mg/hour.	
,	Day 8	1,000 mg		
	Day 15	1,000 mg	Infusions can be started at a rate of 100 mg/hour and increased by 100 mg/hour	
Cycles 2–6	Day 1	1,000 mg	increments every 30 minutes to a maximum 400 mg/hour.	

If a subject experience any grade infusion reaction during infusion, adjust the infusion as outlined below:

- Grade 4 (life threatening): Stop infusion and discontinue therapy.
- Grade 3 (severe): Temporarily interrupt infusion and treat symptoms. Upon resolution of symptoms, restart infusion at no more than half the previous rate (the rate being used at the time that the infusion reaction occurred) and, if subject does not experience any infusion reaction symptoms, infusion rate escalation may resume at the increments and intervals as appropriate for the treatment dose.
- Grade 1 2 (mild to moderate): Reduce infusion rate and treat symptoms. Upon resolution of symptoms, continue infusion and, if subject does not experience any

Ibrutinib + GA101 - Obinutuzumab. University of California, San Diego

infusion reaction symptoms, infusion rate escalation may resume at the increments and intervals as appropriate for the treatment dose.

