6.2.11 Management of Infusion-Related Reactions and Anaphylaxis

Please refer to Section 6.4.4 for information relating to concomitant medications. Medications (including subcutaneous epinephrine, corticosteroids, and intravenous diphenhydramine) and resuscitation equipment should be available for immediate use.

Life-Threatening Infusion-Related Reactions and Anaphylaxis.

In the event of a life-threatening IRR (which may include pulmonary or cardiac events) or IgE-mediated anaphylactic reaction, GA101-Obinutuzumab should be discontinued and no additional GA101-Obinutuzumab should be administered (see Table 3). Subjects who experience any of these reactions should receive aggressive treatment of symptoms and will be discontinued from study treatment. Subjects will continue in follow-up until resolution of reactions or clinical stability.

Table 3 Management of Infusion-Related Symptoms

Infusion-Related Symptoms ^a	Guidance
Grades 1–2	 Interrupt or slow the rate of the infusion Give supportive treatment ^b
	Upon symptom resolution, may resume infusion rate escalation at the investigator's discretion ^c
Grade 3	Discontinue infusion until resolution of symptoms

Ibrutinib + GA101 - Obinutuzumab. University of California, San Diego

- Give supportive treatment ^b
- Upon symptom resolution, may resume infusion rate escalation, at investigator discretion ^c
- Note: If the same adverse event recurs with the same severity, treatment must be permanently discontinued.

Grade 4^d

 Discontinue infusion immediately, treat symptoms aggressively, and do not restart drug

- a Refer to National Cancer Institute Common Terminology Criteria for Adverse Events, v4.0, for the grading of symptoms http://evs.nci.nih.gov/ftp1/CTCAE/CTCAE 4.03 2010-06-14 QuickReference 8.5x11.pdf (Appendix 7)
- Subjects should be treated with acetaminophen and an antihistamine such as diphenhydramine if they have not been received these within the previous 4 hours. IV saline may be indicated. For bronchospasm, urticaria, or dyspnea, subjects may require antihistamines, oxygen, corticosteroids (e.g., 100 mg IV prednisolone or equivalent), and/or bronchodilators. For hypotension, subjects may require vasopressors.
- Upon complete resolution of symptoms, the infusion may be resumed at 50% of the rate achieved prior to interruption. In the absence of infusion related symptoms, the rate of infusion may be escalated in increments of 50 mg/hour every 30 minutes to a maximum rate of 400 mg/hr.

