6.3.3 Ibrutinib Overdose

Any dose of study drug in excess of that specified in this protocol is considered to be an overdose. Signs and symptoms of an overdose that meet any Serious Adverse Event criterion must be reported as a Serious Adverse Event in the appropriate time frame and documented as clinical sequelae to an overdose.

There is no specific experience in the management of ibrutinib overdose in subjects. No maximum tolerated dose (MTD) was reached in the Phase 1 study in which subjects received up to 12.5 mg/kg/day (1400 mg/day). Healthy subjects were exposed to up to single dose of 1,680 mg. One healthy subject experienced reversible Grade 4 hepatic enzyme increases (AST and ALT) after a dose of 1,680 mg. Subjects who ingested more than the recommended dosage should be closely monitored and given appropriate supportive treatment. Refer to Section 11.4.3.8 for further information regarding special reporting situations as a result of overdose

Ibrutinib + GA101 - Obinutuzumab. University of California, San Diego

Dose Modifications and delays for GA101 – Obinutuzumab

Splitting the first dose of GA101 – Obinutuzumab in Cycle 1 is mandatory. The first dose (1,000 mg) must be administered over Days 1 and 2 (100 mg on Day 1 and 900 mg on Day 2). Infusions should be interrupted or slowed if subjects experience infusion reactions (see Section 6.2.11). If a planned dose of GA101 - Obinutuzumab is missed, it should be administered as soon as possible and the next cycle should begin 28 days later. Do not wait until the next planned dose.

No reduction in the dose of GA101 - Obinutuzumab is allowed. A dose delay of up to 8 weeks is permitted for GA101 - Obinutuzumab to allow recovery of hematologic toxicities to \leq Grade 2 or non-hematologic toxicities to Grade 1 or baseline level. If the treatment is delayed for more than 8 weeks because there is no improvement of cytopenia to \leq Grade 2, treatment under this protocol will be discontinued and the subject will continue in follow-up until the beginning of new treatment or death.

If a subject experiences grade 3 or 4 cytopenia, the guidelines for GA101 – Obinutuzumab and Ibrutinib dose-delay are outlined in Table 7:

Table 7 Dose Modification for Cytopenias

Grade	GA101 - Obinutuzumab	Ibrutinib

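### Table 3 note c (Section 6.2.11) allows re-escalation after an infusion reaction with no exception for Cycle 1 Day 1, contradicting the fixed 25 mg/hour rate in Table 1

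*Combined protocol and SAP*

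**What the plan says.** Two sections give rules for the infusion rate.

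- **Section 6.2.6, Table 1.** For the 100 mg dose on Cycle 1 Day 1: "Administer at 25 mg/hour over 4 hours. Do not increase the infusion rate". The rate column is headed as applying "in the Absence of Infusion Reactions/ Hypersensitivity during Previous Infusions". The bullets below the table cover reactions. After a Grade 1-2 or Grade 3 reaction has resolved and symptoms stay away, "infusion rate escalation may resume at the increments and intervals as appropriate for the treatment dose".
- **Section 6.2.11, Table 3.** The Grades 1-2 and Grade 3 rows both point to note c. The Grade 3 row says that after symptoms resolve the subject "may resume infusion rate escalation, at investigator discretion"; the Grades 1-2 row is to the same effect. Note c supplies the numbers: "Upon complete resolution of symptoms, the infusion may be resumed at 50% of the rate achieved prior to interruption". Then, if no infusion-related symptoms are present, "the rate of infusion may be escalated in increments of 50 mg/hour every 30 minutes to a maximum rate of 400 mg/hr".

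Neither Table 3 nor note c mentions Day 1 or refers to Table 1. The obinutuzumab dose-delay text after Section 6.3.3 refers readers to 6.2.11 for interrupting or slowing an infusion. No section says which of the two rules governs.

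**The concern.** Table 1 sets a prohibition for one dose. Note c gives a general permission, and any step it allows breaks that prohibition. Staff who manage a Day 1 reaction from Section 6.2.11 alone find numbers for the restart and the steps, and nothing that holds the rate at 25 mg/hour. A subject who has reacted and recovered could then be infused faster than the rate fixed for a subject who never reacted.

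The first infusion is where the rule would be used most. Section 1.3.4.1 describes reactions as "occurring predominantly during the first hour or shortly after the first infusion". In the pooled CLL monotherapy data in Section 1.3.3, 37 of 38 subjects had an infusion reaction and 11 of 38 had one of Grade 3-4. Those are single-agent studies, so the figures show only that the rule would be needed often. They do not give the rate to expect with this combination, split dose and premedication.

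**Working it through.** **Inputs.** Table 1: Day 1 dose 100 mg, rate 25 mg/hour. Note c: restart at 50% of the earlier rate, steps of 50 mg/hour every 0.5 h, ceiling 400 mg/hour.

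**The plan's own figure.** 100 / 25 = 4.0 h, which matches Table 1.

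**Case A: infusion interrupted, restarted at half rate.** If the reaction occurs t hours into Day 1, the dose left is 100 - 25t mg.

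- Restart: 0.5 x 25 = 12.5 mg/hour. The first 0.5 h delivers 6.25 mg.
- Step 1: 12.5 + 50 = 62.5 mg/hour; 62.5 / 25 = 2.5 times the fixed rate. It is reached if 100 - 25t > 6.25, so t < 3.75 h (the first 225 of 240 minutes).
- The next 0.5 h delivers 31.25 mg, 37.5 mg in all since restart.
- Step 2: 62.5 + 50 = 112.5 mg/hour; 112.5 / 25 = 4.5 times. It is reached if 100 - 25t > 37.5, so t < 2.5 h (the first 150 minutes).

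**Case B: infusion only slowed (Grades 1-2).** For a slowed rate r between 0 and 25 mg/hour, one step gives r + 50, between 50 and 75 mg/hour, which is 2 to 3 times the fixed rate.

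**Time to finish after an interruption at 1 h (75 mg left).**

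| Course after restart | Calculation | Time |
|---|---|---|
| Note c literally, one step only | 0.5 + 68.75 / 62.5 | 1.6 h |
| 12.5 mg/hour for 0.5 h, then back to 25 | 0.5 + 68.75 / 25 | 3.25 h |
| Held at 12.5 mg/hour throughout | 75 / 12.5 | 6.0 h |

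Against one literal step, returning to 25 mg/hour takes 3.25 - 1.6 = 1.65 h longer, and staying at 12.5 mg/hour takes 6.0 - 1.6 = 4.4 h longer.

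**Other days.** On Day 2, Table 1 and note c use the same 50 mg/hour steps. From Day 8, Table 1 uses 100 mg/hour steps, so note c is the slower rule. Take a reaction at 400 mg/hour and a restart at 200, with enough dose left. Note c runs 200, 250, 300 and 350 for 0.5 h each, reaching 400 after 2.0 h and 550 mg. Table 1 steps run 200 and 300 for 0.5 h each, reaching 400 after 1.0 h and 250 mg. The remaining 300 mg at 400 mg/hour takes 0.75 h. The same 550 mg therefore takes 2.0 h or 1.75 h, a difference of 15 minutes.

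**The case against.** The strongest reply is that the protocol, read as a whole, already excludes Day 1. A specific prohibition normally outranks a general permission. The 6.2.6 bullets limit re-escalation to the increments for the dose being given, and the 100 mg dose has none. Table 3 speaks of resuming escalation, and on Day 1 there is nothing to resume. Note c is permissive and conditional: symptoms must have resolved completely before restart, must stay absent before each increase, and the decision is the investigator's. Table 3 also requires permanent discontinuation if the same Grade 3 event recurs at the same severity. Section 6.2.5 requires premedication on Days 1 and 2, and Section 6.2.4 requires close supervision with resuscitation facilities at hand. Section 1.3.4.1 describes most reactions as mild or moderate and resolving with slowing or interruption.

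Most of this stands. It makes literal use of note c on Day 1 less likely and limits the consequences. It does not remove the contradiction: the dose-specific limit is missing from the section that staff consult during a reaction, and the safeguards do not say which rate is allowed. Nor does the heading of Table 1's rate column lift the limit. It refers to reactions during previous infusions, and Day 1 is the first.

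Three stronger readings go too far.

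- A reader might infer that the protocol directs escalation on Day 1. It does not; note c only permits it.
- A reader might infer that the pointer after Section 6.3.3 makes 6.2.11 the governing rule for rates. That pointer concerns interrupting or slowing only.
- A reader might infer more recurrences or DLTs, and so a distorted safety run-in. The documents give no data linking re-escalation rate to recurrence. Section 10.2.4 counts a Grade 3 infusion reaction as a DLT only at re-challenge with permanent discontinuation.

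**Conclusion.** The inconsistency is real and limited. Section 6.2.11 permits, on its face, a Day 1 rate that Table 1 forbids: 62.5 mg/hour after one step from a half-rate restart, 2.5 times the fixed rate. The 4.5-fold figure needs a second discretionary step. These are pump rates, not risks, and no clinical effect can be estimated from the documents. The sample size, type I error and power of both phases are unaffected.

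The conclusion assumes that the note between b and d under Table 3 is the note c cited in both rows, and that 6.2.11 is read without the dose-specific limit in 6.2.6. It is worth correcting because this is a dosing-safety instruction and the correction is small. The documents do not say how many subjects still have Cycle 1 ahead, and the change protects only those. The difference in steps from Day 8 onward is a separate clarity point; a reader might take it for a dosing error, but there note c is simply the slower of two rules.

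**What to change.** Add to note c: *except Cycle 1 Day 1, when the rate after restart may return to, but must never exceed, 25 mg/hour; for other doses follow Table 1 and Section 6.2.6.* The first half settles the safety point and whether a restart at 12.5 mg/hour may go back up to 25. The second half would favor Table 1's 100 mg/hour steps from Day 8 onward, so the sponsor should confirm that choice before adopting it. The Day 1 cap does not depend on it. The 6.2.6 bullets should not be rewritten to 50 mg/hour steps merely for consistency, because that would slow later infusions.

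The cost is one amended clause and an updated infusion order set, with no new procedures, subjects or statistical changes. Day 1 infusion time is unchanged against Table 1. The extra time against note c read literally is at least about 1.65 h for a subject interrupted at 1 h and restarted at 12.5 mg/hour for 30 minutes, with one literal step as the comparator.

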6.3 DOSE MODIFICATIONS AND DELAYS FOR IBRUTINIB AND GA101 – OBINUTUZUMAB

6.3.1 Dose Hold, Reduction, or Discontinuation of Ibrutinib

Treatment with Ibrutinib should be held for any unmanageable, potentially study drug-related toxicity that is Grade 3 or higher in severity. Subjects who require anticoagulant treatment (eg, heparin and/or warfarin) should have study drug hold until stable on anticoagulant therapy.

Ibrutinib may be held for a maximum of 28 consecutive days of toxicity. Ibrutinib should be discontinued in the event of a toxicity > Grade 1 lasting > 28 days.

A hematologic AE grading scheme for hematologic toxicity is included in Appendix 3.

The actions in Table 4 should be taken for the following toxicities:

- Grade 4 ANC (< 500/μL) for > 7 days (Neutrophil growth factors are permitted per ASCO guidelines) (Smith et al., 2006) and use must be recorded in CRF.
- Grade 3 or 4 platelets (< 50,000/µL); or, in subjects with baseline thrombocytopenia, a platelet decrease of 50-74% from baseline in presence of bleeding.

Ibrutinib + GA101 - Obinutuzumab. University of California, San Diego

- Grade 4 Platelets (< 25,000/μL); or, in subjects with baseline thrombocytopenia, decrease of > 75% from baseline or < 20,000/μL, whichever is higher.
 - Grade 3 or 4 nausea, vomiting, or diarrhea, if persistent despite optimal antiemetic and/or anti-diarrheal therapy, or any other Grade 4 toxicity and any unmanageable Grade 3 toxicity.

Table 4 Dose modifications or discontinuation actions for Ibrutinib

Occurrence ≥ G3	Action	
AE		
1 st	Hold Ibrutinib until recovery to Grade ≤ 1 or baseline; may restart	
	at original dose level	
2 nd	Hold Ibrutinib until recovery to Grade ≤ 1 or baseline; restart at	
	one dose level lower (280 mg daily)	
3 rd	Hold Ibrutinib until recovery to Grade ≤ 1 or baseline; restart at	
	one dose level lower (140 mg daily)	
4 th	Discontinue Ibrutinib	

6.3.2 Dose Modifications for Ibrutinib for Hepatic Impaired Subject

Ibrutinib is metabolized in the liver and therefore subjects with clinically significant hepatic impairment at the time of screening (Child- Pugh class B or C) are excluded from study participation.

Subjects while on study who develop significant clinical and/or laboratory signs and/or symptoms of liver dysfunction (e.g., transaminitis, jaundice, etc.) in the opinion of the investigator, should be assessed with the Child-Pugh Score (Table 5) to determine a dose reduction of Ibrutinib as described in Table 6:

Table 5 Child-Pugh Score

The score employs five clinical measures of liver disease. Each measure is scored 1–3, with 3 indicating most severe derangement.

Clinical and Laboratory Criteria	1 Point	2 Points	3 Points
Hepatic	None	Mild to moderate	Severe
encephalopathy		(grade 1 or 2)	(grade 3 or 4)
Ascites	None	Mild to moderate	Severe
		(diuretic	(diuretic
		responsive)	refractory)

Ibrutinib + GA101 – Obinutuzumab. University of California, San Diego

Total bilirubin	<2	2 - 3	>3
(mg/dL)			
Seum albumin	>3.5	2.8 - 3.5	<2.8
(gr/dL)			
International	<1.7	1.7 - 2.3	>2.3
normalized ratio			
(INR)			

Child-Turcotte-Pugh Class obtained by adding score for each parameter (total points)

Class A = 5 - 6 points (mild liver disease)

Class B = 7 - 9 points (moderate liver disease)

Class C = 10 - 15 points (severe liver disease)

Table 6 Dose Modifications for Ibrutinib for Hepatic Impaired Subjects

Child-Pugh Class	Points	Dose Reduction for Ibrutinib
A	5 – 6	280 mg (two capsules)
В	7 – 9	140 mg (one capsule)
С	10 – 15	Hold Ibrutinib until resolved to moderate impairment (Child-Pugh class B) or better

Monitor subjects for signs of toxicity and follow dose modification guidance as needed.

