1.2.4.4 Hemorrhagic Events

There have been reports of hemorrhagic events in subjects treated with ibrutinib, both with and without thrombocytopenia. These include minor hemorrhagic events such as contusion, epistaxis, and petechiae; and major hemorrhagic events, some fatal, including gastrointestinal bleeding, subdural intracranial hemorrhage, and hematuria. Use of ibrutinib in subjects requiring other anticoagulants or medications that inhibit platelet function may increase the risk of bleeding. Subjects with congenital bleeding diathesis have not been studied. See Section 6.4 for guidance on concomitant use of anticoagulants, antiplatelet therapy and/or supplements. See Section 6.5 for guidance on ibrutinib management with surgeries or procedures. In an in vitro platelet function study, inhibitory effects of ibrutinib on collagen-induced platelet aggregation were observed.

Ibrutinib + GA101 – Obinutuzumab. University of California, San Diego

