- 14. Men or women of childbearing potential who refuse to use an adequate measure of contraception (oral contraceptives, intrauterine device, or barrier method of contraception in conjunction with spermicidal jelly) unless they have past medical history of surgical sterilization.
- 15. Vaccination with a live vaccine within 28 days of the initiation of treatment.
 - 16. Concomitant use of warfarin or other Vitamin K antagonists.
- 17. Requirement to receive treatment with a strong cytochrome P450 (CYP) 3A inhibitor. Subjects who received a strong cytochrome P450 (CYP) 3A inhibitor within 7 days prior to the first dose of Ibrutinib or subjects who require continuous treatment with a strong CYP3A inhibitor.
- 18. Subjects with chronic liver disease with hepatic impairment (Child-Pugh class B or C).

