6.4.2.4 Antiplatelet Agents and Anticoagulants

Warfarin or vitamin K antagonists should not be administered concomitantly with Ibrutinib. Supplements such as fish oil and vitamin E preparations should be avoided. Use Ibrutinib with caution in subjects requiring other anticoagulants or medications that inhibit platelet function. Subjects with congenital bleeding diathesis have not been studied. Ibrutinib should be held at least 3 to 7 days pre- and post-surgery depending upon the type of surgery and the risk of bleeding (see Section 6.5).

Subjects requiring the initiation of therapeutic anticoagulation therapy (other than warfarin or a vitamin K antagonist) during the course of the study should have treatment with ibrutinib/ placebo held, the sponsor's medical monitor should be contacted, and ibrutinib/placebo should not be restarted until the subject is clinically stable and the reinitiation of ibrutinib/placebo is approved by the sponsor's medical monitor. Subjects should be observed closely for signs and symptoms of bleeding. No dose reduction is required when study drug is restarted.

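### Section 6.3.1 implies that ibrutinib may resume in a subject stable on warfarin, while Section 6.4.2.4 says the two should not be given together

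*Combined protocol and SAP*

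**What the plan says.** Two sections of the protocol tell the investigator what to do when a subject on treatment needs an anticoagulant.

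- **Section 6.3.1**, on holding, reducing or stopping ibrutinib: "Subjects who require anticoagulant treatment (eg, heparin and/or warfarin) should have study drug hold until stable on anticoagulant therapy". The sentence stands alone. It has no reference to another section and no separate provision for vitamin K antagonists.
- **Section 6.4.2.4**, on antiplatelet agents and anticoagulants, opens with: "Warfarin or vitamin K antagonists should not be administered concomitantly with Ibrutinib". It then sets a hold-and-restart route for "Subjects requiring the initiation of therapeutic anticoagulation therapy (other than warfarin or a vitamin K antagonist) during the course of the study". On that route ibrutinib "should not be restarted until the subject is clinically stable and the reinitiation of ibrutinib/placebo is approved by" the sponsor's medical monitor.

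Two other places bear on intent. Exclusion criterion 16 in Section 4.2, repeated in the synopsis, reads "Concomitant use of warfarin or other Vitamin K antagonists". Section 1.2.4.4, on hemorrhagic events, says: "See Section 6.4 for guidance on concomitant use of anticoagulants, antiplatelet therapy and/or supplements".

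**The concern.** For a subject started on warfarin during the study, the two sections point in opposite directions. Section 6.3.1 implies that ibrutinib comes back once warfarin is stable. Section 6.4.2.4 implies that it does not come back while warfarin continues.

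What is at stake is bleeding. Section 1.2.4.4 reports major hemorrhage with ibrutinib, some of it fatal, and adds: "Use of ibrutinib in subjects requiring other anticoagulants or medications that inhibit platelet function may increase the risk of bleeding". Section 11.3.3 makes major hemorrhage an adverse event of special interest. An investigator who relied on 6.3.1 alone could create the combination that 6.4.2.4 advises against. The same investigator would also miss the medical monitor's approval, which 6.4.2.4 requires before restart even with a permitted anticoagulant.

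**Working it through.** No figure in the plan depends on this point, so the check is a comparison of text.

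**1. What the hold in 6.3.1 means.** The section does not use the word restart. It does give the hold an end point: stability on anticoagulant therapy. A subject who has reached that point is still taking the anticoagulant. The natural meaning is that ibrutinib resumes alongside it, and the named examples are heparin and warfarin.

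**2. Side by side.**

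| Question | Section 6.3.1 | Section 6.4.2.4 |
|---|---|---|
| Which anticoagulants does the hold cover? | All anticoagulant treatment, with warfarin named | Therapeutic anticoagulation other than warfarin or a vitamin K antagonist |
| What ends the hold? | Stability on the anticoagulant | Clinical stability plus medical monitor approval |
| May ibrutinib be given with warfarin? | Implied yes, once stable | Should not be |
| Reference to the other section? | None | None |

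The last two end conditions for a permitted anticoagulant are compatible: 6.3.1 omits the approval step but does not contradict it. For warfarin the two sections conflict.

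**3. Does the rest of the protocol resolve it?** Largely, as to intent. Criterion 16 keeps warfarin users out at entry, and Section 1.2.4.4 sends readers to Section 6.4 for anticoagulants. But criterion 16 governs entry, whereas 6.3.1 governs subjects already on treatment, and the pointer sits in the background chapter rather than in 6.3.1.

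**4. Would an investigator reach 6.3.1 without 6.4.2.4?** This is plausible. Section 1.2.4.5 says that for persistent atrial fibrillation the investigator should weigh risks and benefits and follow the dose-modification guidelines. Section 10.2.5 and Table 7 both identify 6.3.1 as the place for ibrutinib dose modification. Sections 1.2.4.1 and 1.2.4.2 list atrial fibrillation among serious events reported in at least 2% of subjects, with monotherapy and with combinations. Anticoagulation for such an event is my assumption. The documents do not say how often it would be started or with which drug.

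**5. How many subjects?** Planned enrolment is 32, which is the ceiling before any replacements, and the floor is zero. Only subjects who start warfarin while on study are affected. With no rate in the documents, the range cannot be narrowed by calculation, but the entry exclusion makes a small number likely.

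**The case against.** The strongest reply is that the conflict exists only by implication and that the protocol already signposts the answer. Section 6.3.1 orders a hold and never says that warfarin and ibrutinib may be combined. Section 6.4.2.4 is the more specific section, expressly covers anticoagulation begun during the study, and excludes warfarin from the restart route. Section 1.2.4.4 points to Section 6.4 on this very subject. An investigator who follows both sections will not give the two drugs together.

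Most of this stands, and it limits the consequence. A reader might infer that the protocol leaves open which section governs. The documents do not support that: there is no formal precedence clause, but the pointer and the on-study wording of 6.4.2.4 identify the intended rule. A reader might also count how often warfarin is mentioned and treat the tally as a measure of the problem. It is not one. The synopsis and Section 4.2 print the same criterion, and the two mentions in 6.4.2.4 belong to one rule, so a count says nothing about the number of subjects or the risk to each.

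It is also fair to say that 6.4.2.4 is worded as advice (should not), sits under the heading for medications to be used with caution, and that warfarin is absent from the prohibited list in Section 6.4.3. Calling warfarin formally prohibited on study would go too far.

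The reply does not remove the implied permission in 6.3.1. That section is where an investigator looks for hold and restart rules, and it sends the reader nowhere else.

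**Conclusion.** The point holds as an internal inconsistency in the dosing rules. Section 6.3.1, read as written, leads to the wrong action for a subject on warfarin, and 6.4.2.4 is the rule the protocol intends. It should be corrected because the consequence is a bleeding risk that the protocol itself describes and the correction is nearly free.

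The size is modest. The conflict reaches only subjects who start warfarin on study and whose investigator applies 6.3.1 without 6.4.2.4. That number is probably small and cannot be estimated from the documents. The two-stage design, the response endpoint and the planned analyses are untouched.

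The conclusion rests on one reading: that holding a drug until the subject is stable on an anticoagulant means resuming it while the anticoagulant continues. I see no other natural reading.

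**What to change.** In Section 6.3.1, remove warfarin from the example, keep the hold for all anticoagulant treatment, and add the reference. For instance:

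> *Study drug should be held in any subject who requires anticoagulant treatment (eg, heparin) and restarted only as described in Section 6.4.2.4; ibrutinib should not be resumed while the subject is receiving warfarin or another vitamin K antagonist.*

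This keeps the strength of the existing advice (should not) and does not narrow the present hold to therapeutic anticoagulation; neither change is needed to remove the conflict. One side effect should be accepted knowingly: the approval step in 6.4.2.4 is written for therapeutic anticoagulation, and the reference would apply it to every anticoagulant hold under 6.3.1.

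The sponsor may also wish to say what happens to a subject who needs warfarin long term: a change of anticoagulant, a continued hold, or discontinuation of ibrutinib. The 28-day limit in 6.3.1 is written for toxicity holds and does not settle this.

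The cost is one sentence at the next amendment, with no added visits, tests or subjects.
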